## 1.0 PROTOCOL REVISION HISTORY

Protocol Revision Number	Protocol Revision Date
A	14 January 2020

### 3.3 CLINICAL SITES

The registry will be conducted in European countries including Austria, Germany, Italy, Poland, France, Switzerland and United Kingdom. The Sponsor will maintain a list of principal investigators and investigational sites for the duration of the registry; the definitive list of sites will be provided with the final clinical investigation report of the registry.

## 4.0 PROTOCOL SYNOPSIS

Title:	HARPOON™ System: ReaL world outcomes from a multiCenter observATional European registry (REPLICATE)
Protocol Number:	2019-12
Sponsor	HARPOON™ Medical, an indirect wholly owned subsidiary of Edwards Lifesciences Corporation
Design:	A single arm, prospective, multicenter, post-market, observational registry
Objective:	To collect data on the HARPOON™ Mitral Valve Repair System for use in patients with severe degenerative mitral regurgitation due to posterior leaflet prolapse.
Device:	HARPOON™ Beating Heart Mitral Valve Repair System
Population:	Patients who undergo mitral valve repair surgery with the HARPOON™ Beating Heart Mitral Valve Repair System as part of standard of care treatment for severe degenerative mitral regurgitation due to mid- segment posterior leaflet prolapse
Enrollment:	Approximately 150 implanted subjects, including up to 30 subjects enrolled after the HARPOON surgery (capped at 5 subjects per site)
Definition of Enrollment:	A subject is considered enrolled upon providing a signed informed consent
Registry Sites:	Up to 50 sites in Europe
Follow-up:	Clinical and imaging assessments at baseline/pre-procedure, procedure, discharge, 30 days, 1-year and annually thereafter through 5 years post-implant, per local standard of care
Outcome Measures:	Freedom from re-operation due to recurrent severe mitral regurgitation through 1-year post-implant
Statistical Analysis:	No planned statistical hypothesis testing will be performed within this REPLICATE Registry protocol. Descriptive and summary statistical analysis will be provided for baseline/pre-procedure, procedure and outcome variables.

## 5.0 ABBREVIATIONS

AE	Adverse event
CA	Competent authority
CE	Conformité Européene
CEC	Clinical Events Committee
CKD	Chronic kidney disease
CRF	Case report form
EC	Ethics Committee
ECL	Echo Core Laboratory
EDC	Electronic data capture
EFS	Early Feasibility Study
eCRF	Electronic case report form
ePTFE	Expanded polytetrafluoroethylene
GCP	Good clinical practice
ID	Identity Number
ISO	International Organization for Standardization
LTFU	Lost to follow-up
MDD	Medical Device Directive
MR	Mitral Regurgitation
MVRS	Beating Heart Mitral Valve Repair System
NYHA	New York Heart Association
OR	Operating Room
PA	Pulmonary Artery
PEC	Patient Eligibility Committee
SAE	Serious Adverse Event
SOC	Standard of Care
TOE	Transoesophageal Echocardiogram
TTE	Transthoracic Echocardiogram
USADE	Unanticipated Serious Adverse Device Effect

## 6.0 INTRODUCTION AND BACKGROUND

### 6.1 DEVICE DESCRIPTION

The HARPOON™ Beating Heart Mitral Valve Repair System, known hereafter as HARPOON System, is described in detail in the Instructions for Use (IFU). The IFU will be provided to the sites and Ethics Committees (ECs), and a copy included in the Trial Master File and Investigator Site File.

#### 6.1.1 REGULATORY STATUS

The HARPOON System is CE-marked. Its use in this registry is consistent with the product's labelling.

#### 6.1.2 INDICATION FOR USE

The HARPOON System is intended to reduce the degree of mitral regurgitation (MR) in patients with severe MR caused by mid-segment posterior leaflet prolapse as a result of degenerative mitral valve disease by delivering and anchoring Expanded polytetrafluoroethylene (ePTFE) chords to the prolapsed mitral valve leaflet in a beating heart.

#### 6.1.3 TECHNICAL DESCRIPTION OF THE DEVICE

The HARPOON System consists of two parts: 1) HARPOON Introducer and 2) HARPOON Delivery System. Both items are essential for proper delivery of ePTFE implants in the mitral valve leaflet to eliminate or reduce mitral valve regurgitation. The HARPOON System is a Class III product following rule 8 of the Annex IX of the MDD 93/42/EEC (intended to be used to deliver an implant in direct contact with the heart). For a detailed description of the HARPOON System, please refer to the HARPOON™ Beating Heart Mitral Valve Repair System Instructions for Use (IFU).

## 6.2 PRIOR CLINICAL EXPERIENCE WITH THE HARPOON SYSTEM: EFS AND CE MARK TRIALS

Two (2) ongoing European clinical trials have assessed the safety and performance of the HARPOON System: the Early Feasibility Study (EFS) and the CE Marking Trial (CE Mark, conducted under two (2) clinical protocols):

The purpose of the EFS trial is to assess the safety and performance of the HARPOON System (previously the Harpoon Medical TSD-5 Device). The early data collected from the trial were used to power and support the design of the study to support CE Mark of the HARPOON System. The purpose of the CE Marking trial is to assess the safety and performance of the HARPOON System in subjects with severe degenerative mitral regurgitation by implanting ePTFE chords in the posterior leaflet of the mitral valve via transapical access thereby obviating the need for open surgery and its risks.

This clinical experience summary is based on clinical data as of 02 April 2019 for subjects enrolled from 16 February 2015 (first enrolment in EFS) to 07 November 2017 (last enrolment in CE Mark).

Sixty-five (65) subjects were enrolled at six (6) investigational sites between both studies. This includes thirteen (13) subjects enrolled in the EFS study and fifty-two (52) subjects in the CE Mark study. Of the enrolled population, sixty-two (62) subjects were implanted with the HARPOON System (thirteen (13) in the EFS trial and forty-nine (49) in the CE Mark Trial). Three patients left the operating room without the investigational device. One case was aborted before the Harpoon procedure and 2 cases were converted to standard of care (SOC) mitral valve surgery. Overall, follow-up compliance of 100% (56/56) of eligible subjects was achieved at the 1-year visit. Six (6) HARPOON System subjects were censored through 1-year including two (2) deaths and four (4) reoperations. Follow-up compliance of 98% (40/41) has been achieved so far at the 2-year visit; nine (9) subjects have yet to reach their 2-year follow-up window. Follow-up is currently ongoing.

### **6.2.1 SAFETY ENDPOINTS**

One (1) early (1.6%) and two (2) late (2.0%/pt-yr) deaths have been reported. The CEC has adjudicated one (1) early death with primary cause of death as cardiac arrest, and not related to the study device. One of the two (2) late deaths was adjudicated as caused by aortic dissection and device related, and the second late death was a sudden death with unknown causality, and therefore was also counted as device related. One (1) early (1.6%) and ten (10) late (10.1%/pt-yr) reoperations have been reported, including nine (9) repairs and two (2) mitral valve replacements.

There were no reports of unanticipated adverse device effects.

### **6.2.2 PRIMARY PERFORMANCE RESULTS**

In the EFS study, procedural success was defined as the subject leaving the operating room with at least one (1) ePTFE chord in place, having a discharge MR grade of  $\leq$  mild and 30-Day MR grade  $\leq$  mild, without a reoperation prior to 30 days. Procedural success was achieved in 84.6% (11/13) of the enrolled cohort.

In the CE Mark study, procedural success was defined as the subject leaving the operating room with at least one (1) ePTFE chord in place, having a discharge MR grade of  $\leq$  moderate and 30-Day MR grade  $\leq$  moderate, without a reoperation prior to 30 days. Procedural success was achieved in 88.5% (46/52) of the enrolled cohort.

### **6.2.3 SECONDARY PERFORMANCE RESULTS**

#### **6.2.3.1 MITRAL REGURGITATION**

Severity of mitral regurgitation (MR) was evaluated by the Echo Core Lab at the baseline, discharge, 1-month, 6-month, 1-year, and 2-year follow-up visits for the HARPOON System cohort. At 2-year follow up, 65.8% (25/38) of patients had mitral regurgitation of mild or less, 26.3% (10/38) of patients had moderate MR and 7.9% (3/38) of patients had severe MR.

Several subjects with moderate to severe mitral regurgitation underwent re-operations and were identified as having ruptured ePTFE chords. An investigation was conducted to determine the root cause of ePTFE chord ruptures. The root cause of the chord ruptures was found to be over-tensioned chords. Findings confirmed that no material or device design changes were required. As a result of this investigation, screening and procedural updates to the IFU, Training Program Materials, and Post Market Clinical Follow-up Study were made to mitigate future ePTFE chord ruptures.

#### **6.2.3.2 NYHA FUNCTIONAL CLASS**

Performance was also assessed using NYHA functional classification change. At 1 year of follow-up, 92.3% of subjects were in NYHA class I, 5.8% were in NYHA class II, and 1.9% were in NYHA class III, corresponding to an improvement (50%) or maintenance (48%) of NYHA class for 98% (51/52) of subjects.

### **6.2.4 SUMMARY**

The results of the EFS and CE Marking trials support the safety and performance of the HARPOON System. Patient follow-up is ongoing.

## **7.0 REGISTRY DESIGN**

### **7.1 OBJECTIVE**

The objective of this registry is to collect data on the HARPOON™ Mitral Valve Repair System for use in patients with severe degenerative mitral regurgitation due to posterior leaflet prolapse.

## **7.2 DESIGN**

The design is a single arm, prospective, multicentre, post-market observational registry.

## **7.3 OUTCOME MEASURES**

The key outcome measure is freedom from re-operation due to recurrent severe mitral regurgitation through 1-year post-implant.

## **7.4 NUMBER OF SUBJECTS**

Approximately 150 implanted subjects, including up to 30 subjects enrolled after the HARPOON surgery (capped at 5 subjects per site) will be included in this registry.

# **8.0 REGISTRY POPULATION**

The registry population will comprise of subjects (over 18 years of age) who undergo mitral valve repair surgery with the HARPOON™ Beating Heart Mitral Valve Repair System per the IFU as part of standard of care treatment for severe degenerative mitral regurgitation due to mid- segment posterior leaflet prolapse, and who are willing to participate in the registry and provide signed informed consent for the collection and use of their data.

## **8.1 SCREENING AND ENROLMENT**

Subjects who are clinically suitable for treatment with the HARPOON System, as per the IFU, will be evaluated for inclusion in the registry.

Subjects who agree to participate must sign an Ethics Committee (EC)-approved informed consent and will be considered part of the enrolled population.

As outlined in section 7.4, up to 30 subjects may be enrolled after undergoing the HARPOON surgery, capped at 5 subjects per site. Subjects that have already been implanted with the HARPOON device will be asked to sign an EC-approved informed consent to enroll in the registry to allow collection of the data on their HARPOON surgery and data through 5 year follow-up.

A subject is considered enrolled upon providing a signed informed consent.

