**Table 1 - Data Collection Schedule**

	Baseline/ Pre-Procedure	Procedure	Discharge	30 Days  (+14 days)	1 Year  (+/- 30 days)	2-5 Years  (+/- 45 days)
Informed Consent	X					
Medical History	X					
TOE	X	X				
TTE 			X	X	X	X
NYHA Functional Class	X				X	
SAE that results in a death, ADE, SADE, USADE, device deficiency and device malfunction assessment 	X 	X	X	X	X	X

All follow-up dates will be calculated from the date of the implant procedure. Follow-up visits may be conducted in person (preferred) and via telephone.

Enrolled subjects for whom the implant procedure was prematurely aborted, or the HARPOON procedure was attempted but device not implanted will be followed for 30 days or until resolution of any adverse events related to the implant procedure and then exited from the registry.

TTE should be performed at 30 days, 1 year and annually through 5 year follow up or per local standard of care if TTE frequency or requirements are different from study schedule.

Safety event reporting will start at the time of enrollment, i.e. subject providing a written informed consent, through 5-year follow-up.

Only SAE that results in a death is applicable for reporting at Baseline/Pre-Procedure time point.

Abbreviations: ADE=adverse device effect; NYHA=New York Heart Association; SADE=serious adverse device effect; SAE=serious adverse event; TOE=transesophageal echocardiography; TTE=transthoracic echocardiography; USADE=unanticipated serious adverse device effect.

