## 10.0 STATISTICAL METHODS

The analysis population will consist of the subjects who were enrolled and undergone a mitral valve repair surgery with the HARPOON System, regardless of procedure outcome. The analysis population excludes any subjects who signed the registry consent but were exited from the study prior to the procedure.

There is no planned statistical hypothesis testing within this REPLICATE Registry protocol. Descriptive and summary statistical analysis will be provided for baseline/pre-procedure, procedure and outcome variables.

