## 11.3 REPORTING ADVERSE EVENTS

### 11.3.1 REPORTING BY THE INVESTIGATOR

As outlined above, reporting of applicable adverse events to the sponsor is the Investigator's responsibility and will start at time of enrolment and will continue until closure of the registry follow-up at 5 years post procedure or until a subject exits the registry.

The investigator shall notify the sponsor immediately and no later than 3 calendar days after the investigator or designated site personnel has become aware of an SAE that results in a death, SADE, USADE or device deficiency/device malfunction by completing the Adverse Event eCRF, or the Device Deficiency eCRF. Non-serious ADE should be reported to the sponsor as soon as possible upon the investigator or designated site personnel becoming aware of the event.

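### If the post-implant consent route is used, pooling late with pre-procedure enrollees tends to understate deaths and non-implants; Section 10 should report by consent timing, and the start of event recording needs reconciling

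*Combined protocol and SAP*

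**What the plan says.** All references are to the combined protocol and SAP.

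- **Late route.** Section 7.4 sets the target at about 150 implanted subjects, "including up to 30 subjects enrolled after the HARPOON surgery (capped at 5 subjects per site) will be included in this registry". Section 8.1 describes the route: "Subjects that have already been implanted with the HARPOON device will be asked to sign an EC-approved informed consent to enroll in the registry", with the purpose "to allow collection of the data on their HARPOON surgery and data through 5 year follow-up". Neither section sets a maximum time from implant to consent or requires consecutive enrolment.
- **Time origin.** Table 1, footnote 1: "All follow-up dates will be calculated from the date of the implant procedure".
- **Analysis set.** Section 10.0 takes "subjects who were enrolled and undergone a mitral valve repair surgery with the HARPOON System, regardless of procedure outcome". It plans no split, adjustment or sensitivity analysis by consent timing.
- **Non-implants.** Section 9.5 keeps enrolled subjects whose procedure was aborted, or attempted without implant, for 30 days or until related events resolve.
- **Start of event recording.** Table 1, footnote 4: "Safety event reporting will start at the time of enrollment, i.e. subject providing a written informed consent, through 5-year follow-up". Section 11.0 agrees, and Section 11.3.1 says that reporting "will start at time of enrolment and will continue until closure of the registry follow-up at 5 years post procedure". Section 9.6.2 separately has the cause of any surgical valve intervention entered in the EDC and does not tie this to consent.
- **Key outcome.** Section 7.3 names freedom from re-operation for recurrent severe MR through 1 year after implant.

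**The concern.** A patient must be alive to sign. One who consents some months after implant could not have died in those months and still been enrolled, yet that time is counted from implant. Similarly, someone already implanted cannot be a non-implant, whereas a pre-procedure enrollee can. Late enrollees therefore add to both denominators without being able to supply the early part of either numerator. Both effects favour the device, and neither shrinks as enrolment grows if the late share stays the same.

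The plan has no hypothesis test, so the descriptive figures are its product. Deaths are collected (Sections 9.4.2 and 11.0), and Section 6.2.1 gives the prior trials' deaths as early and late. A reader could well set the registry's figures beside those.

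The key outcome raises a different question: would a re-operation between implant and late consent be recorded, and may such a patient enrol late at all?

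**Working it through.** **Inputs from Sections 6.2 and 6.2.1.** 65 enrolled and 62 implanted. Three left theatre without the device: one aborted before the procedure and two converted. By 1 year there were 2 deaths and 4 re-operations, with one early event of each kind.

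**The documents' own figures reproduce.** 65 − 3 = 62; 62 − 6 = 56 eligible at 1 year; early death 1/62 = 1.6%.

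**Assumptions.** All 30 late places are used (30/150 = 20%). Early events fall by day 30 and the rest are spread evenly to day 365. Late enrollees have the same risk after consent as other survivors. All prior re-operations are treated as if for recurrent severe MR.

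**1-year death.** Let d = 2/62 = 3.23%, and let d(c) be the part of d falling before consent day c. For c of 30 or more, d(c) = 1/62 + [(c − 30)/335] × 1/62. The pooled rate is

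0.8 d + 0.2 (d − d(c)) / (1 − d(c)).

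| Late consent at | d(c) | Late enrollees' rate | Pooled | True |
|---|---|---|---|---|
| implant | 0 | 3.23% | 3.23% | 3.23% |
| 30 days | 1.61% | 1.64% | 2.91% | 3.23% |
| 6 months | 2.35% | 0.90% | 2.76% | 3.23% |
| 12 months | 3.23% | 0 | 2.58% | 3.23% |

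With 15 late enrollees (10%) the pooled figure is 3.07% at 30 days and 2.90% at 12 months. For 30-day death, if all 30 consent after day 30, it is 0.8 × 1/62 = 1.29% against 1.61%.

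**Left theatre without the device.** 120 pre-procedure implants imply 120 × 65/62 = 125.8 attempts, of which 5.8 are non-implants. Adding 30 late implants gives 5.8/155.8 = 3.7%, against 3/65 = 4.6%. If the case aborted before the procedure is not counted, 120 × 64/62 = 123.9 attempts give 3.9/153.9 = 2.5%, against 2/64 = 3.1%. Neither result depends on the consent interval.

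**Sampling error.** The 95% half-width is 1.96 √(r(1 − r)/n). At n = 150 it is 2.8 points for 1-year death, 2.0 for 30-day death and 3.9 for re-operation. The base rates are themselves weak: exact 95% intervals are 0.4% to 11.2% for 2/62 and 1.0% to 12.9% for 3/65.

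**Key outcome, by reading.** Let p = 4/62 = 6.45%, with p(c) defined like d(c) but with 3/62 spread over days 30 to 365.

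- If late enrollees are all re-operation-free at consent: 0.8 p + 0.2 (p − p(c)) / (1 − p(c) − d(c)) = 6.16% at 30 days, 5.72% at 6 months and 5.16% at 12 months.
- If re-operated patients may enrol and their events are recorded: 0.8 p + 0.2 p / (1 − d(c)) = 6.47% to 6.49%, which is essentially no shift.

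Sections 8.1 and 9.6.2 point to the second reading as far as recording goes. Table 1 footnote 4 and Sections 11.0 and 11.3.1 leave room for the first. No passage says whether a patient already re-operated may enrol late.

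**The case against.** **The effect is conditional.** This stands. The route allows up to 30 subjects, so it may go unused, and consent within days of surgery would leave mortality almost untouched. A reader might infer that any use of the route understates mortality; the documents do not support that. Nor is the net direction for 1-year death certain. With consent at 30 days, late enrollees would show no shift if their later risk were 3.2% rather than 1.6%, and with no consecutive-enrolment rule they could be sicker or healthier than average. Only the loss of deaths before consent has a fixed direction.

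**The key outcome is not shown to be biased.** This also stands. It is tempting to read the start-at-consent wording as proof that earlier re-operations are lost. But Section 8.1 is the specific rule for late enrollees and covers their surgery and follow-up, and Section 9.6.2 gives re-operations their own route to the EDC. What remains is ambiguity.

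**Pooling is not less accurate.** One might infer that pre-procedure enrollees must be the primary set. A simulation of 1-year death (20,000 runs, 120 pre-procedure and 30 late, consent uniform over days 30 to 365) gave a root mean squared error of 1.41 points pooled, 1.61 for pre-procedure only and 1.56 with delayed entry. At this size the choice trades bias against precision.

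**The affected summaries are secondary.** Mortality is not a named outcome, no procedural-success outcome is defined, and no comparison with the prior trials is planned. This lowers the severity. It does not remove the point, because a confidence interval would not reveal a shift of this kind.

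**Conclusion.** The point holds in conditional form. If late enrolment is used, the pooled summaries understate, in expectation, (a) deaths, given a real implant-to-consent gap and similar risk afterwards, and (b) non-implants, whatever the gap. At full use and the prior point rates, the shifts are 0.3 to 0.6 points for 1-year death and 0.9 points for non-implant (0.6 if only conversions count). Both are well inside sampling error and rest on 2 deaths and 3 non-implants.

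For the key outcome, the finding is an unclear recording rule together with an unstated eligibility question, and no bias is demonstrated. The textual facts are firm; the net size is not. Severity: minor to the low end of should-fix.

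**What to change.** **Section 10.0**

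- Show mortality, procedural, 30-day and key 1-year results by consent timing: pre-procedure, post-procedure and pooled.
- Report the share leaving theatre without the device on pre-procedure enrollees.
- Tabulate the implant-to-consent interval.
- Optionally, add a sensitivity analysis for survival with delayed entry at consent.

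**Section 8.1 and Table 1, footnote 4**

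- State that, once a late enrollee has consented, events from implant to consent are recorded retrospectively. Bring Sections 11.0 and 11.3.1 into line.
- State whether patients already re-operated may enrol late, and reconcile this with the registry exit rules in Sections 9.5 and 9.6.2. Under those rules, such a patient could meet an exit criterion on entry.

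**Cost.** This takes a few lines of text and some extra abstraction for at most 30 subjects; no visit or sample-size change is needed. Intervals are wider in the subgroups: for 1-year death the half-width is 3.2 points at n = 120 against 2.8 at n = 150, and the late group of at most 30 will be very imprecise on its own. Keeping the pooled figure alongside preserves its precision.

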# **9.0 REGISTRY PROCEDURES AND SCHEDULE OF ASSESSMENTS**

## **9.1 SCHEDULE OF ASSESSMENTS**

Clinical and echocardiographic data available from routine clinical assessments will be collected for the following time points: Baseline/pre-procedure, Procedure, Discharge, 30 days, 1 year and annually through 5 years. It is expected that the institutions' standard-of-care for the management of patients undergoing mitral valve repair surgery will be aligned and consistent with established guidelines and recommendations and may include the assessments described below.

